The workbook went through health literacy editing with a goal of a 5th grade reading level. The chapters ranged from 3rd to 7th grade levels. It was felt that it was important for subjects to learn or at least be exposed to words that were kidney related and frequently used by their health care providers. So the first time each of these words were used in the workbook they were red and the definition was in the kidney talk section on that page. Then the first time the word appeared in subsequent chapters the word was in red but no definition was on that page.

Subjects will be randomized into 1 of 2 education arms that offer various levels of support or a control arm using a site specific computer generated randomization schedule. Presumed monthly visits.

Study Arm	Handouts	Visit 1*	Visit 2	Visit 3	End of Study June 2022
Testing		Pre-test		Post-Test	Evaluation
1: Case Study Model	Workbook Action Plan (V1) Label reading Exercise (V2)	Pharmacist initiated review of workbook and assist with Action Plan goal selection	Action Plan Reinforcement. Discuss Chapters 1-4. Provide “Label Reading Exercise”	Action Plan Reinforcement. Discuss Chapters 5-8 and resources. Review results of Label exercise	Open conversations from each party for all arms after evaluation
2: Minimal Instruction	Workbook Action Plan	Briefly explain handouts with focus on Action Plan.(5-10 minutes)	Action Plan Reinforcement. Answer patient’s questions.	Action Plan Reinforcement. Answer patient’s questions.	As Above
3: Control	Resource List Action Plan	Answer patient’s questions.	Answer patient’s questions.	Answer patient’s questions.	As Above

*On first visit, education arms subjects will be asked to read 1 chapter of the workbook weekly. All subjects will receive a CKD Action Plan and be asked to set individual goals.

Secondary outcome data collected at each visit include both self-reported and/or

Title: Pragmatic Approach to Chronic Kidney Disease Education in the Delta V.6

PI: [name]

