pharmacist or physician confirmed blood pressure and AIC, eGFR, hemoglobin. Patient and/or pharmacist initiated CKD conversation and topics including CKD action plan goal progress. The action plan has 1 knowledge goal related to CKD cause, eGFR and trend and 10 performance goals based on international guidelines and best practices including AIC goal of 7 or less, blood pressure goal of less than 140/90, exercise goal of 30 minutes 5 times a week, medications that may need to be avoided (ex: ibuprofen) or may need to be taken (ex: Statin) if you have CKD and DM or over 50 years old), smoking cessation, kidney friendly diet (may need to modify salt, phosphorus and/or protein intake and be edema free [may require monitoring and adjust salt and water intake], home monitoring of blood pressure, blood sugar and weight, weight management and anemia (goal hemoglobin above 10g/dL)

Study Population

High Risk Subjects will be identified from the Harps MTM program or others having multiple known medical problems (CKD, HTN, DM or heart disease). Know Your Kidney Number Posters which will be available statewide by the time the study starts will be posted in the pharmacy. Even though they are not study specific, they provide pertinent CKD information that could motivate subjects to want to learn more about how to protect their kidneys. Study Patient information Sheets will be available for interested parties.

A total of 100 clusters of 1 or more people from familial or peers groups will be enrolled. The actual number of subjects will depend on the volume of clusters with more than 1 person. This would include approximately 1/3 of the Harps MTM subjects that have both DM and HTN.

Inclusion Criteria

- Adults (any gender)>18 years old
- Enrolled in Harp's MTM program
- Has Known CKD or 2 of the 3 conditions covered in MTM (DM, HTN and Heart Failure)
- Not on dialysis

Exclusion Criteria

- unable to read or speak English
- history of significant cognitive dysfunction unless qualified caregiver is the one being educated
- not personally independent or without any social support

Risks and Benefits

A risk to study participants is the potential for loss of confidentiality of study data.

Measures to protect the confidentiality of study data will be implemented as described in the Data Handling and Recordkeeping section below.

Title: Pragmatic Approach to Chronic Kidney Disease Education in the Delta V.6

PI: [name]

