Know workbook, slide sets, CKD action plan, Label reading exercise, Web-based resource list, data collection sheets, pre and post tests and program evaluation. UAMS staff will participate in the initial education of Harps staff and future education, as requested. UAMS will make the 10 points of CKD Care for Primary Care Providers (PCPs) available to both Harps staff and local PCPs, as requested.

Harps oversight staff and UAMS research staff will have monthly web-based or face to face meetings, with additional communication as needed.

Reporting requirements are the same for each site and outlined in the data section above. A central site may be selected by Harps when the sites are selected and serve as a model or mentoring site.

Data Analysis

Study arms will be compared by RRT choice using logistic regression that includes covariates found to differ between the groups. Results will be reported in terms of odds ratios and their 95% confidence intervals. Each group will be compared on the ability to choose a modality by the end of their 2nd or 3rd MTM visit, depending on their study arm and at the end of the study (June 2022) by comparing pre and post testing and program evaluation answers. To ensure balance in patient characteristics across clusters chi-square or Fisher's exact test, as appropriate, will be used to evaluate categorical measures, whereas two-sample t-test or Wilcoxon rank test, as appropriate, will be used for continuous measures.

The primary study aim is the ability of the participants to choose a dialysis modality by the end of their second or third visit, depending on their study arm. Descriptive statistics will be used to examine the trend in the patients' ability to choose a dialysis modality, level of interest in kidney transplant, the selection of a possible donor and having enough information to decide across the two assessment periods.

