Secondary outcomes will be compared in all clusters. Because randomization seldom results in samples that are balanced on all baseline characteristics, information on control variables relevant to choice of dialysis mode will be collected, including age, gender, baseline intent to start home based dialysis, whether currently being followed by a nephrologist, patient engagement measured by the percent of visits where CKD patient initiated discussion took place and self-reported and provider confirmed outcomes listed in study plan. Pharmacists and staff time will be compared between arms and linked to costs to support each intervention arm. Tests appropriate for the measure will be used when comparing baseline characteristics between the research arms.

The sample size was based on what was appropriate for what could be reasonably be accomplished in the time frame with the available funding. Power based on the primary aim was a secondary consideration. A population of 100 clusters could result in a much larger population of subjects depending on the size of the clusters. Utilizing clusters to essentially train peer educators and describe their training methods, as well as, the outcomes of each of their cluster members can inform future research involving CKD peer educator led CKD patient education programs.

Ethical Considerations

This study will be conducted in accordance with all applicable government regulations and University of Arkansas for Medical Sciences research policies and procedures. This protocol and any amendments will be submitted and approved by the UAMS Institutional Review Board (IRB) to conduct the study.

This study meets the criteria for exempt review and does not require formal consent of the subjects. However, a Patient Information Sheet explaining the study will be provided to interested parties. After discussion with Harp's pharmacist, verbal consent will be obtained and completion of the pre-test will be evidence of consent. UAMS will receive no HIPAA data on subjects. All data will be de-identified as outlined above and a HIPPA waiver has been requested.

Dissemination of Data

Results of this study may be used for presentations, posters, or publications. The publications will not contain any identifiable information that could be linked to a participant.

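### A measure that accrues after randomisation is listed among the baseline control variables, and nothing keeps it out of the primary model

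*Combined protocol and SAP*

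**What the plan says.** All references are to the combined protocol and SAP.

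- **Data Analysis, primary model.** Renal replacement choice is compared between arms by "logistic regression that includes covariates found to differ between the groups". The section gives no covariate list, no threshold for a difference and no restriction to baseline values. The accompanying tests are introduced with "To ensure balance in patient characteristics across clusters".
- **Data Analysis, control variables.** The reason given is "Because randomization seldom results in samples that are balanced on all baseline characteristics". The variables are described as bearing on the choice of dialysis mode, which is the primary outcome. The list runs through age, gender, baseline intent and nephrologist care, and then adds "patient engagement measured by the percent of visits where CKD patient initiated discussion took place" and "self-reported and provider confirmed outcomes listed in study plan". The paragraph ends: "Tests appropriate for the measure will be used when comparing baseline characteristics between the research arms".
- **Study Design and Procedures, visit data.** The text after the visit table begins "Secondary outcome data collected at each visit include both self-reported and/or" and includes "Patient and/or pharmacist initiated CKD conversation and topics including CKD action plan goal progress". The same section has pharmacists and staff track the discussions that patients start, by topic and time.

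**The concern.** A percentage of visits cannot exist before the visits take place. Visit 1 does not supply a baseline value either, because the visit table starts arm-specific contact there: pharmacist-led review in Arm 1, a short explanation in Arm 2, and answers to questions only in the control arm. Engagement so measured is a possible consequence of the arm.

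The entry rule makes this worse. A variable enters when it differs between groups. A baseline variable in a randomised trial differs only by chance, but engagement may differ because the arm changed it, and that is when adjusting for it is wrong for the total effect. Two things then happen. Any part of the effect that runs through engagement is removed. And if unmeasured motivation drives both patient questions and modality choice, conditioning on engagement brings in bias even when the arm has no effect on choice.

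A smaller point concerns the outcomes in the same list. Blood pressure, A1C, eGFR and hemoglobin are recorded at enrolment and again at each visit. Enrolment values are sound for adjustment and follow-up values are not. The text does not say which are meant.

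**Working it through.** **Step 1: can the text put engagement in the model?**

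| Question | What the Data Analysis section gives |
|---|---|
| Is engagement named as a control variable? | Yes |
| Is the list tied to the primary outcome? | Yes, by the reference to choice of dialysis mode |
| What admits a covariate to the primary model? | An observed difference between groups |
| Is admission limited to baseline values? | No |
| Does any sentence exclude engagement? | No |

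The closing sentence on baseline comparisons says which tests will be used. It does not restrict the model.

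**Step 2: how much could it matter?** The documents give no engagement rate, no expected arm difference and no effect size, so there is no figure of the plan's to reproduce. Every input below is an assumption unless marked.

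- Motivation U ~ N(0,1), unmeasured.
- Engagement E = Binomial(3, expit(bE·U + s·arm))/3. The three visits come from the visit table. Control engagement averages 50%, because expit(0) = 0.5 and U is symmetric.
- logit P(choice) = a + tau·arm + bY·U + g·E, with a set so that 30% of the control arm make the choice.
- With bE = 1, s = ±0.5 shifts mean engagement by about 10 percentage points and s = ±1 by about 20.

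**(a) Trial scale, no true effect (tau = g = 0).** There are 33 subjects per arm (100 clusters ÷ 3 arms, one person each, equal allocation), bE = 1 and 10,000 replicates per setting. Engagement enters if a t-test gives p < 0.05.

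Engagement enters in about 5% of trials with no shift, 23-24% with a 10-point shift and 67-69% with a 20-point shift.

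False-positive rates, with Monte Carlo SE about 0.002-0.003:

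| bY | s | Unadjusted | Entry rule | Always adjusted |
|---|---|---|---|---|
| 0.5 | -1 | 0.047 | 0.053 | 0.056 |
| 0.5 | -0.5 | 0.045 | 0.045 | 0.049 |
| 0.5 | +0.5 | 0.049 | 0.049 | 0.050 |
| 0.5 | +1 | 0.049 | 0.058 | 0.061 |
| 1 | -1 | 0.047 | 0.072 | 0.085 |
| 1 | -0.5 | 0.047 | 0.048 | 0.057 |
| 1 | +0.5 | 0.045 | 0.046 | 0.057 |
| 1 | +1 | 0.046 | 0.073 | 0.084 |

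The true odds ratio is 1.00. Its geometric mean under the entry rule, over all trials, is:

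- 10-point shift: 1.06-1.09 if the arm lowers engagement, 0.96-0.91 if it raises it.
- 20-point shift: 1.17-1.37 or 0.84-0.74.

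The SE of the log odds ratio is 0.57-0.61. The largest average bias is ln(1.37) = 0.31, and 0.31/0.61 to 0.31/0.57 is 0.51 to 0.54 standard errors.

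**(b) Large sample, real effect (tau = 0.5, bE = 1), computed by quadrature.** Risk differences are used because they are free of non-collapsibility. The direct effect is averaged over both arms' engagement distributions, and the adjusted model is standardised to pooled engagement. The mild case has |s| = 0.5, g = 0.75, bY = 0.5. The strong case has |s| = 1, g = 1.5, bY = 1.

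| Case | Total (points) | Direct | Adjusted for engagement |
|---|---|---|---|
| Mild, arm raises engagement | 12.0 | 10.4 | 8.5 |
| Strong, arm raises engagement | 13.8 | 8.7 | 2.3 |
| Mild, arm lowers engagement | 8.6 | 10.2 | 12.1 |
| Strong, arm lowers engagement | 2.7 | 8.0 | 14.0 |
| Mild, no shift | 10.3 | 10.3 | 10.3 |
| Strong, no shift | 8.3 | 8.3 | 8.3 |

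Total minus direct is lost mediation, and direct minus adjusted is common-cause bias. Taken before rounding, these are 1.6 and 2.0 points in the mild case and 5.2 and 6.4 in the strong case when the arm raises engagement.

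With no shift the odds ratio still moves on adjustment, from 1.58 to 1.62 (mild) and from 1.45 to 1.57 (strong). That is non-collapsibility and not bias.

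**The case against.** The strongest reply is that no sentence places engagement in the primary model. The control variables are only to be collected, their stated purpose is baseline balance, and the paragraph ends with baseline comparisons. Read generously, the covariates that differ are baseline characteristics. The paragraph also opens with secondary outcomes, so the list may not be meant for the primary model alone. This stands in so far as the plan does not commit the error. It does not close the gap: the sentence that speaks of baseline imbalance itself names engagement and ties the list to the primary outcome.

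The second reply is that harm needs several undocumented steps. The analyst must admit engagement, the arm must shift it, and either a common cause or mediation must be present. That is correct. With a 10-point shift the entry rule shows no detectable inflation of false positives; visible inflation needs a 20-point shift and mainly the stronger common cause.

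Three cautions on the numbers also stand:

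- The entry-rule averages include trials where engagement never entered. Among trials where it did, the strongest 20-point cases give about 1.46 or 0.71, roughly 0.6 of a standard error.
- The simulation treats subjects as independent and ignores clusters of more than one person.
- The strong large-sample case shows what the assumptions imply and is not a forecast for this trial.

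Finally, enrolment values are the natural reading of the listed outcomes. That is fair, and the same sentence can confirm it.

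**Conclusion.** The concern holds as a minor ambiguity. The plan names a post-randomisation measure as a control variable for the primary outcome, and its covariate rule has no baseline limit. Following the text can therefore put a consequence of the arm into the primary model.

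Neither the size nor the direction of the result can be derived from the documents. If the arm does not shift engagement, adjustment introduces no bias. If it does, the estimate may move either way. Under the assumptions above, the distortion is modest against sampling error in a pilot sized for feasibility. It is not a threat to the trial, and it is not shown that the primary odds ratio will be biased.

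**What to change.** Add to both the primary-model and control-variable paragraphs of Data Analysis:

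> Adjustment covariates in the primary model are limited to values recorded before randomisation or, at the latest, before any arm-specific contact at Visit 1. Patient-initiated discussion and follow-up values are not covariates in the primary model.

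Any enrolment variable already in the plan may still qualify, including baseline intent and enrolment blood pressure, A1C, eGFR and hemoglobin. The limit applies however the baseline covariates are chosen. Selecting them by observed difference is a separate matter that this sentence does not address.

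Report engagement by arm as a descriptive process outcome. A mediation analysis is not needed; if one is done, label it exploratory and keep it apart from the primary result.

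The cost is wording only. Data collection does not change, and engagement is still tracked and reported. If exclusion was always intended, the sentence simply records it.

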Harp's pharmacists will screen patients in their MTM program and enroll them in familial or peer clusters consisting of 1 or more subjects and randomize them into 1 of the 4 study arms using a site specific randomization schedule. Each arm will receive pre and post testing and health literacy evaluation. Two education arms will use the 139 page CKD: What You Need to Know workbook including the CKD Action Plan as self-study tools and follow-up during regular MTM appointment. The 3 arms include 2 education arms and a control arm with various levels of intervention: Arm 1) case management model including pharmacist initiated discussion of workbook content and action plan reinforcement, Arm 2) brief introduction of the workbook and action plan reinforcement, Arm and Arm 3) the control group will receive a list of web-based CKD sites and a copy of the action plan with no additional intervention. Patient initiated CKD discussions will be tracked by both the pharmacist and staff by topic and time spent. Time spent by the pharmacist and staff will be calculated along with outcomes and compared in each group. Data collected upon enrollment will include year of birth, race, gender, county of residence, history of CKD, diabetes, hypertension and/or heart failure, patient reported blood pressure, AIC, eGFR and hemoglobin, smoking history, renal transplant history and if is under the care of or has been seen by a nephrologist in the past.

The CKD: What You Need to Know Workbook is 139 pages and includes:

- An Introduction
- 8 Chapters plus resources:
 1. Kidneys and Chronic Kidney Disease (CKD)
 2. Protecting Your kidneys and Slowing CKD Progression
 3. Your Choices for Dialysis and Transplantation
 4. Lab Results: What they mean & What you can control
 5. Chronic Kidney Disease & Eating Habits

6. Chronic Kidney Disease & Meds
7. Learning to Cope with Kidney Disease
8. Paying for Your CKD Treatment
9. CKD Action Plan
10. Web-based Resources
11. Kidney Talk: What do these words mean?
12. Resources

Each section ends with “Frequently Asked Questions”, “Test Your Knowledge” and has space for notes. Patient testimonies are found at the back of 6 chapters.

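### The engagement score depends partly on who opens the CKD discussion, which the protocol sets by arm, so it is liable to read low in Arm 1 and should not be compared between arms as engagement

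*Combined protocol and SAP*

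**What the plan says.** The Data Analysis section of the combined protocol and SAP states that "information on control variables relevant to choice of dialysis mode will be collected". Its list includes "patient engagement measured by the percent of visits where CKD patient initiated discussion took place". There is one definition for all arms, and no type of visit is excluded.

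Study Design and Procedures describes "Arm 1) case management model including pharmacist initiated discussion of workbook content and action plan reinforcement". In the visit table of that section:

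- **Arm 1.** Visit 1 is "Pharmacist initiated review of workbook and assist with Action Plan goal selection". Visit 2 begins "Action Plan Reinforcement. Discuss Chapters 1-4". Visit 3 follows the same pattern with Chapters 5 to 8.
- **Arm 2.** Staff briefly explain the handouts at Visit 1. At Visits 2 and 3 they reinforce the Action Plan and take the patient's questions.
- **Control.** The only entry at each of the three visits is to answer what the patient asks. The table's footnote adds that every subject receives an Action Plan and is asked to set goals.

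On recording, the same section says "Patient initiated CKD discussions will be tracked by both the pharmacist and staff by topic and time spent". The secondary outcome data collected at each visit include "Patient and/or pharmacist initiated CKD conversation and topics including CKD action plan goal progress". The Data Analysis section then says that secondary outcomes are compared across all clusters.

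**The concern.** The score counts visits at which the patient opened a CKD discussion. How often a patient has the chance to do so depends on how much CKD talk the staff have already opened, and the protocol sets that by arm. The chance is smallest in Arm 1 and largest in control. No rule says how to score a subject's own question when it is raised inside a pharmacist-led discussion.

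Two equally engaged subjects can therefore receive different scores because of their arm alone. Initiation is listed among the secondary outcome data, and secondary outcomes are compared. A reader of the results could conclude that the most intensive education arm had the least engaged patients when there was no true difference. The protocol presents patients as proactive partners in their care, so such a conclusion would mislead on a theme the study cares about.

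**Working it through.** The plan gives no expected engagement rate, significance level or power, so there is no figure of its own to reproduce. What follows is an illustration.

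**Inputs from the documents**

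- Three scheduled visits in each arm (visit table). The Data Analysis text refers to the second or third visit depending on arm, so the denominator is not fully settled. Three is used here.
- 100 clusters (Study Population). Split equally over the three arms of the visit table, this gives 100/3, or about 33 per arm. The equal split is an assumption.

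**Assumed inputs**

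- p: the chance that a subject would raise CKD at a visit if nobody else had, equal in all arms.
- q: the chance that a staff-led opening pre-empts this.
- One person per cluster, all visits attended, visits independent, and a two-sided 5% test.

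**Expected score**

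Control scores p and Arm 1 scores p(1 − q). The relative bias is [p − p(1 − q)]/p = q. With p = 0.4:

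| q | Control | Arm 1 |
|---|---|---|
| 0.25 | 40% | 0.4 × 0.75 = 30% |
| 0.5 | 40% | 0.4 × 0.5 = 20% |
| 1 | 40% | 0% |

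**Chance of a false significant difference, Arm 1 versus control**

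With constant p across visits, a subject's score has variance p(1 − p)/3. The standard error (SE) of the difference is the square root of the sum of the two arm variances divided by 33. The rejection probability is approximately Φ(difference/SE − 1.96).

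- q = 0.5: SE = √[(0.24/3 + 0.16/3)/33] = 0.0636. The difference is 0.20, the ratio 3.15, and the probability Φ(1.19) ≈ 0.88. Simulated t-tests gave 0.87.
- q = 0.25: SE = √[(0.24/3 + 0.21/3)/33] = 0.0674. The difference is 0.10, the ratio 1.48, and the probability Φ(−0.48) ≈ 0.32.

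**If control Visit 1 is also pre-empted**, because of the goal setting in the footnote:

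- q = 0.5: the control mean is (0.2 + 0.4 + 0.4)/3 = 0.333. SE = √{[(0.16 + 0.24 + 0.24)/9 + 0.16/3]/33} = 0.0614. The difference is 0.133, the ratio 2.17, and the probability Φ(0.21) ≈ 0.58.
- q = 0.25: the control mean is (0.3 + 0.4 + 0.4)/3 = 0.367. SE = √{[(0.21 + 0.24 + 0.24)/9 + 0.21/3]/33} = 0.0667. The difference is 0.067, the ratio 1.00, and the probability Φ(−0.96) ≈ 0.17.

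**Varying engagement between subjects.** A simulation that drew each subject's underlying rate from a Beta(2,2) distribution, with mean 0.5, and did not pre-empt control visits gave 35% at q = 0.25 and 89% at q = 0.5. At q = 0 it gave 5%, the nominal level.

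**The case against.** The strongest reply is that the plan does not prevent an Arm 1 patient from being counted. It logs "Patient and/or pharmacist initiated CKD conversation and topics including CKD action plan goal progress", so both parties can be recorded at one visit, and patient-initiated discussions are tracked by topic and time with no arm excluded. This stands. A reader might infer that an Arm 1 subject who asks questions during a chapter review must score zero, but the documents do not say so. That is only the extreme case q = 1.

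A second reply is that the visit table summarises scheduled content and does not ration questions. This also stands. A count of visits with room for patient questions, such as none of three in Arm 1 and three of three in control, would over-read it. Control Visit 1 is partly staff-opened through goal setting, and all three Arm 2 visits are partly staff-opened. The contrast between arms is one of degree.

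Third, Arm 1 scores might be higher in practice, because reading and discussing the workbook may prompt questions. That is possible, but it does not rescue the score, which cannot separate a real rise in engagement from a change in who speaks first.

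Fourth, the percentage is named as a control variable and not as a secondary endpoint. What is listed as secondary outcome data is conversation and topics by initiator. This limits the weight of the point. It does not remove it, because the initiation data are still among the outcomes to be compared.

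**Conclusion.** The concern holds as a minor point. The score partly measures how the intervention is delivered, so for equally engaged subjects it is liable to be depressed in Arm 1 relative to control. The direction needs only q above 0. The size rests wholly on assumed values: at p = 0.4, 33 single-person clusters per arm and q of 0.25 to 0.5, a false difference would be called significant in roughly 30% to 90% of trials. If control Visit 1 is equally pre-empted, the figures fall to about 17% and 58%.

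Two stronger conclusions are not supported. A reader might infer that the trial will show Arm 1 as least engaged. The documents give neither p nor q, and the workbook may act in the other direction. A reader might also infer that the artefact will bias the primary odds ratio, since the model is a "logistic regression that includes covariates found to differ between the groups". The text leaves that route open but does not settle it: the balance tests are described for patient and baseline characteristics, and this score is collected during follow-up. Whether it belongs in the primary model is a separate question.

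The severity is minor because this is a pilot with a sample size set by feasibility, and the score is named only as a control variable.

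**What to change.** In the Data Analysis section, state that who initiated CKD discussion is reported descriptively within each arm as intervention delivery, and is neither compared between arms nor interpreted as a difference in engagement. Make the list of control variables agree with that sentence.

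In Study Design and Procedures, add one recording rule for all arms: a CKD question or topic that the subject raises is logged as patient-raised, even within a pharmacist-led discussion. The rule should be in place before data collection, since such questions cannot be reliably reconstructed afterwards.

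A score built from this log would still need caution. Longer Arm 1 discussions give more chances to ask, so counting every patient-raised topic could favour Arm 1. It should not become a new between-arm measure of engagement.

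The cost is two sentences and a small staff judgement about whether a question was the subject's own. The trial also gives up any between-arm claim about engagement from these data.

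### Lab values that some subjects may not have can enter the primary logistic regression through the imbalance rule, and the plan has no rule for missing covariate values

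*Combined protocol and SAP*

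**What the plan says.** The first paragraph of Data Analysis compares arms on choice of renal replacement therapy by "logistic regression that includes covariates found to differ between the groups". It names the tests used to look for differences but gives no threshold.

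Later in the same section, the plan says that "information on control variables relevant to choice of dialysis mode will be collected". The list covers age, gender, baseline intent for home dialysis, nephrologist follow-up, engagement, and the "self-reported and provider confirmed outcomes listed in study plan".

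Study Design and Procedures shows what those outcomes are. At enrollment the plan collects "patient reported blood pressure, AIC, eGFR and hemoglobin". At each visit the same four measures are self-reported and/or confirmed by a pharmacist or physician.

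The same section says of the Action Plan: "The action plan has 1 knowledge goal related to CKD cause, eGFR and trend". The main entry condition under Inclusion Criteria is "Has Known CKD or 2 of the 3 conditions covered in MTM (DM, HTN and Heart Failure"; no lab value is required. No study blood draw is described. No analysis set and no method for missing covariates is stated.

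**The concern.** Whether a lab enters the primary model depends on an observed imbalance, and nothing ensures that every subject has a value for it. A subject can enter with hypertension and heart failure, without diabetes or known CKD, and may have no A1C or eGFR to report. eGFR is also something the study sets out to teach, so it is foreseeable that some subjects cannot state it at Visit 1.

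Standard logistic regression software removes any record with a missing covariate, and nothing in the plan prevents that. An imbalance on one lab could then change who is in the primary analysis. The estimate would lose precision and would describe subjects with known labs. Those subjects may be better informed, which bears on an outcome about being able to choose a modality. The sample size was set by feasibility, so there is little room for avoidable loss.

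**Working it through.** The plan states no power, significance level, selection threshold or missing-lab rate, so it has no figure to reproduce. What follows is illustrative, and the assumptions are marked.

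**Inputs**
- 100 clusters of one or more people (Study Population).
- Three arms (visit table in Study Design and Procedures).
- Three candidate labs: A1C, eGFR and hemoglobin.
- Assumed: every cluster is one person and allocation is equal, so 100/3 ≈ 33 per arm. This is the smallest-sample case.
- Assumed: labs independent of one another, and a 5% threshold for a difference.
- Assumed: 30% or 50% of subjects lack a given lab.

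**Step 1. Chance that at least one lab is selected under pure randomisation**
- One test per lab across arms: 1 − 0.95³ = 0.143, about 14%.
- Two-sample tests in all three arm pairs: in 20,000 simulated trials with arms of 33, 33 and 34, a single lab was flagged in 12.0% and at least one of three in 31.5%. As a check, 1 − (1 − 0.120)³ = 0.319. The range is therefore about 31% to 32%.
- The threshold is not stated. With one test per lab at 10% or 20%, the chance becomes 1 − 0.90³ = 0.271 or 1 − 0.80³ = 0.488.

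**Step 2. Cost if one lab is selected and the fit uses complete records only**

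The retained number is n(1 − m), where m is the share missing. The confidence interval on the log odds ratio widens by 1/√(1 − m), taking subjects as independent and the outcome rate as unchanged.

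| Assumed share missing | Per arm, from about 33 | Widening of 95% CI |
|---|---|---|
| 30% | 33.3 × 0.7 ≈ 23 | 1/√0.7 = 1.20 |
| 50% | 33.3 × 0.5 ≈ 17 | 1/√0.5 = 1.41 |

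**Step 3. Cost if all three labs are selected**

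At 30% missing on each, 70 of 100 subjects remain if the same people lack all three. If the gaps are independent, 100 × 0.7³ ≈ 34 remain. Selection of all three by chance is much rarer than selection of one, so this is an outer case.

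**Step 4. Cost if no lab is selected**

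Nobody is dropped for this reason. Under the Step 1 assumptions at 5%, that is about 86% of trials with one test per lab (1 − 0.143), or 68% to 69% with pairwise tests.

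**The case against.** The strongest reply is that the labs are only candidates. The plan says that information on them will be collected, and the model admits only covariates on which the arms differ. A reader might infer that A1C, eGFR and hemoglobin are fixed terms in the primary model and that subjects will certainly be lost. The documents do not support that, and Step 4 shows that usually none is lost by this route.

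A reader might also infer that many subjects will lack these values. No document gives a rate. The eGFR knowledge goal shows what is taught, not how many records are blank. Visit values may be confirmed by a pharmacist or physician, so a patient's not knowing a value does not mean that the study lacks it. This stands, with a limit: confirmation is optional, and the enrollment list names patient report only. Filling a baseline gap from a later visit would adjust for something measured after randomisation.

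Third, the plan does not prescribe a complete-record analysis. Omission is the software default, and it matters only because the plan is silent. If the missing values are baseline values, the subjects who remain are still compared by randomised arm. The established harm is therefore to precision and to whom the result applies. That the remaining subjects are better informed is plausible, not shown.

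Fourth, clusters may hold several people, so 33 per arm is a lower figure and the real sample may be larger. The relative widening at a given missing share does not depend on the starting number.

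Finally, the enrollment list asks "if is under the care of or has been seen by a nephrologist in the past", while the control variable is "whether currently being followed by a nephrologist". A reader might infer that the two are recorded as one combined answer, so that current follow-up cannot be recovered. The Intake Sheet is not in the documents, and the prose fits two separate fields equally well. That inference is not supported.

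**Conclusion.** The point holds as a conditional weakness. Labs that eligibility does not require are candidates for the primary model, selection rests on observed imbalance with no stated threshold, and no rule covers missing values. If a lab is selected, an ordinary fit omits subjects without it.

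The chance of selecting at least one is about 14% to 32%, depending on how the tests are done, given independent labs and a 5% threshold. The cost if one is selected is an interval about 1.20 times wider at 30% missing and 1.41 times wider at 50%. Both missing rates are assumptions; the true rate is unknown and could be lower. The documents do not support a claim of certain loss or of a biased comparison between arms. The change is worth making because a better rule is available at almost no cost.

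**What to change.** In both places in Data Analysis, replace selection by observed imbalance with a short, prespecified set of Visit 1 covariates that every subject answers. Suitable items are age, gender, pre-test modality choice or intent, history of CKD, history of diabetes, and nephrologist care. Keep A1C, eGFR and hemoglobin for description.

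If a lab is kept in the model, name it in advance, use its baseline value only, fill missing values with the overall mean, and add a missing-value indicator. State that every randomised subject with an outcome is analysed.

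The cost is a few sentences in the plan. The downside is that a chance imbalance on a lab is either not adjusted for, or is adjusted for only through a simple imputation.
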